15.1 Primary Aim

The primary aim is to determine if a 16-week intervention based on aerobic conditioning, specificity of training, and muscle overload for strengthening (the PUSH intervention) is more successful in producing community ambulation at 16 weeks post-randomization than an intervention of transcutaneous electrical nerve stimulation, flexibility, and AROM exercises (the PULSE intervention). Therefore, the one-sided null hypothesis that the PUSH intervention does not result in a higher proportion of community ambulators 16 weeks post-randomization will be tested. This hypothesis will be tested at five time points based on a Z-statistic (which is equivalent to the square root of the Pearson chi-square statistic). The critical values for each time point were chosen to preserve an overall type-1 error rate of 0.025.²⁰⁶ If the exploratory analyses reveal data sparseness (expected frequency less than 5 for at least one combination of treatment group and community ambulation status), Fisher's exact test will be performed instead of using the chi-square statistic. The difference in proportions with a 95% confidence interval will also be reported.

The binary outcome variable will be ability to walk at least 300 meters in six minutes (yes/no). This variable will take the value of 'yes' if the participant was tested with the SMWT and walked 300 m or more in six minutes. This variable will take the value of 'no' if 1) the participant was tested with the SMWT and walked less than 300 m in six minutes or 2) the participant was not tested with the SMWT (or the participant was tested but not according to protocol) and adjudication resulted in the participant's being classified as a treatment failure (see 11.5 for description of the adjudication procedure). Participants whose adjudication result is 'indeterminate' will be excluded from the primary analysis.

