15.5 Interim Analyses

Interim analyses will be conducted by an alpha and lower bound spending design. At the time of this update, we have already performed an interim analysis based on the first 28.6% of the data. We plan to perform three additional interim analyses (based on the first 40%, 60%, and 80% of data available), where the boundary values for early stopping will be evaluated using the Hwang-Shih-Decani spending function approximation to the O'Brien-Fleming alpha-spending function [$\gamma = -4$ for lower-bound alpha spending (inefficacy/harm), and $\gamma = 4$ for upper-bound alpha spending (efficacy)].^{211,212} The upper and lower bounds will be computed for a test of efficacy with one-sided nominal $\alpha = 0.025$. For example, when testing for efficacy ($\delta > 0$) at the first interim analysis, $Z > 3.09$ would denote efficacy, and $Z < -1.76$ would denote inefficacy/harm. Table 4 shows the anticipated proportion of the sample accrued at each of the remaining interim analyses along with the corresponding critical values for declaring significance (or lack thereof) at each time point. The critical values are subject to change if the actual information available at the time of the analysis differs from the expected information available. These critical values were calculated using the gsDesign package in R version 2.10.1.

Table 4. Anticipated Critical Values for Each Planned Analysis

Analysis	Expected % of information available	Critical z-value for upper-bound alpha spending (for efficacy)	Critical z-value for lower bound alpha spending (for inefficacy/harm)
First interim analysis	28.6%	3.09	-1.76
Second interim analysis	40%	3.03	-1.57
Third interim analysis	60%	2.69	-0.97
Fourth interim analysis	80%	2.37	-0.21
Final analysis	100%	2.03	2.03

The spending function applies specifically to analysis of the primary outcome (community ambulation at 16 weeks post-randomization). However, at each interim analysis, study performance and secondary and tertiary outcomes will be examined to aid in the interpretation of the primary outcome results.

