Statistical Analysis Plan

Improving Community Ambulation after Hip Fracture (CAP)

Study Chair and Principal Investigator:

[name], MSHyg

Supported by: The National Institute on Aging (*R01 AG035009*)

ClinTrials Registration number: NCT01783704
December 1, 2017

Version 12.0
October 19, 2016

Statistical Analysis Plan for CAP

This document is based on section 15 of the protocol but it provides additional details so that the analysis plan is completely specified. In the process of adding details, the DCC decided to change some of the analysis plans as described in the next section.

Summary of changes from the original plan that was in the protocol.

The table below provides a summary of the differences between this detailed statistical analysis plan and the plan that was in the protocol.

Analysis Question	Original Plan	Additional details and/or changes in the plan
Primary Outcome (Community Ambulation)		
Primary analysis of Primary outcome: comparison of treatment groups with respect to CAP (Section 1.1.1)	Chi-Square test or Fisher's Exact Test if data are sparse. Cutoffs for significance based on interim monitoring plan. 95% confidence interval for difference between groups in the proportion of community ambulators	No change in statistical tests. Details added regarding construction of confidence intervals for differences in proportions: If the p-value is based on Chi-Square, we will use standard asymptotic intervals. If it is based on Fisher's Exact test, we will use exact intervals.
Sensitivity analysis of conclusions about primary analysis due to nonrandom missingness of the outcome. (Section 1.1.2)	Not in original plan	Published method developed by Magder
Secondary analysis of primary outcome: slightly revised outcome definition, and adjustment for rates of indeterminate outcome data. (Section 1.1.2)	Weighted estimating equations to account for rates of indeterminate outcomes in the two treatment groups	We propose modifying the strategy of choosing weights. Rather than basing the weights on risk of missing outcomes, we will base the weights on imbalances between the groups, whatever the cause. Candidate variables for weights are listed. We will rank the potential weighting variables by a published method (Beach and Meier), and choose a number to include based on a rule of thumb regarding the number of covariates a model can have.

Analysis Question	Original Plan	Additional details and/or changes in the plan

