Analyses for all aims will be performed according to the intention-to-treat (ITT) paradigm. Prior to confirmatory analysis, exploratory data analyses will be performed. These exploratory analyses will consist of histograms for continuous outcomes to examine whether a transformation is needed to meet modeling assumptions and frequencies for categorical data to assess whether the data are sparse. With the exception of the statistical test of the primary hypothesis, all statistical tests will be two-sided and will not be adjusted for multiple comparisons. As described in greater detail below, the test of the primary hypothesis (comparing the groups with respect to proportion who are community ambulators at 16 weeks) will be based on a one-sided 0.025-level hypothesis test procedure performed at five time points throughout the trial.

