1.1 Primary Outcome

1.1.1 Primary Analysis of Primary Outcome.

The primary aim is to determine if a 16-week intervention based on aerobic conditioning, specificity of training, and muscle overload for strengthening (the PUSH intervention) is more successful in producing community ambulation at 16 weeks post-randomization than an intervention of transcutaneous electrical nerve stimulation, flexibility, and AROM exercises (the PULSE intervention). Therefore, the one-sided null hypothesis that the PUSH intervention does not result in a higher proportion of community ambulators 16 weeks post-randomization will be tested. This hypothesis will be tested at five time points based on a Z-statistic (which is equivalent to the square root of the Pearson chi-square statistic). The critical values for each time point were chosen to preserve an overall type-1 error rate of 0.025. Table 1 shows the critical values:

Table 1. Critical Values for Each Planned Analysis

Analysis	Expected % of information available	Critical z-value for upper-bound alpha spending (for efficacy)	Critical z-value for lower bound alpha spending (for inefficacy/harm)
First interim analysis	28.6%	3.09	-1.76
Second interim analysis	40%	3.03	-1.57
Third interim analysis	60%	2.69	-0.97
Fourth interim analysis	80%	2.37	-0.21
Final analysis	100%	2.03	2.03

If the exploratory analyses reveal data sparseness (expected frequency less than 5 for at least one combination of treatment group and community ambulation status), Fisher's exact test will be performed instead of using the chi-square statistic. A 95% confidence interval will be constructed for the probability of community ambulation in each group by inverting two one-sided tests based on the binomial distribution. If the primary analysis p-value is based on the Z-statistic, then a confidence interval for the difference in community ambulation between the two groups will be constructed using standard asymptotic methods. If the primary analysis is based on Fisher's exact test, then an exact 95% confidence interval will be constructed for the difference in probabilities using the method of Chan and Zhang (Chan ISF, Zhang Z 1999) as implemented in SAS.

The binary outcome variable will be ability to walk at least 300 meters in six minutes (yes/no). This variable will take the value of 'yes' if the participant was tested with the SMWT and walked

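### The primary difference is tested with five-look sequential bounds but reported with a fixed-sample 95% interval, which covers somewhat below 95% over the design and can disagree with the final test

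*SAP*

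**What the plan says.** SAP Section 1 describes the primary test as a "one-sided 0.025-level hypothesis test procedure performed at five time points throughout the trial". SAP 1.1.1 adds that "The critical values for each time point were chosen to preserve an overall type-1 error rate of 0.025". Its Table 1 lists efficacy bounds of 3.09, 3.03, 2.69, 2.37 and 2.03, with lower bounds of -1.76, -1.57, -0.97 and -0.21 at the four interim looks. The last row reads "Final analysis 100% 2.03 2.03". On timing, protocol 15.5 states that "we have already performed an interim analysis based on the first 28.6% of the data" and plans "three additional interim analyses (based on the first 40%, 60%, and 80% of data available").

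The interval is treated separately. Protocol 15.1: "The difference in proportions with a 95% confidence interval will also be reported". SAP summary of changes: "If the p-value is based on Chi-Square, we will use standard asymptotic intervals". SAP 1.1.1 repeats this for the Z-statistic branch: "then a confidence interval for the difference in community ambulation between the two groups will be constructed using standard asymptotic methods". For the Fisher branch it gives an exact 95% interval.

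Neither document mentions a repeated, stagewise or otherwise sequentially adjusted interval, a confidence level matched to 2.03, an estimator for use after early stopping, or a rule for when test and interval disagree. The SAP says it was written to specify the analysis completely, and interval construction is among the details it added. This is therefore a stated choice, not an omission.

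**The concern.** The test allows for repeated looks and the interval does not. A fixed-sample interval (estimate ± 1.96 SE at whichever look ends the trial) has 95% coverage only if the stopping time does not depend on the data. Two consequences follow. First, over the whole design, coverage falls below its label. Second, at the final look a result with Z between 1.96 and 2.03 fails the prespecified test while the reported interval excludes zero. The primary paper would then show a negative decision beside an interval that reads as positive, with no rule to settle it. In addition, the plan has no estimation rule for an early efficacy stop, where the ordinary estimate is too large on average.

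**Working it through.** **Inputs.** Information fractions 0.286, 0.4, 0.6, 0.8 and 1, with the bounds in SAP Table 1. From protocol 15.6.1: 105 per group, 6.8% loss, 12.2% non-compliance, 16% vs 36%. *Assumption:* standard asymptotic means the unpooled Wald interval. The documents do not say whether the lower bound is binding, so both cases are shown.

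**Reproducing the plan.** Hwang-Shih-DeCani spending with parameter -4 for both bounds gives upper bounds 3.091, 3.032, 2.693, 2.374 and 2.025, and lower bounds -1.763, -1.566, -0.967 and -0.208. These match Table 1. (Protocol 15.5 prints +4 for the upper bound; nothing here depends on that.) The rounded bounds give one-sided type I error 0.0248, against 0.025 stated.

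**Design alternative.**
- Evaluable per arm: 105 × 0.932 = 97.86.
- Diluted PUSH rate: 0.16 + 0.20 × 0.878 = 0.3356. Difference: 0.1756.
- Pooled rate: 0.2478. Pooled SE: √(2 × 0.2478 × 0.7522 / 97.86) = 0.0617.
- Drift (true difference divided by final-look SE): 0.1756 / 0.0617 = 2.845.
- Simulated power at this drift is 80.1%, against the 80% in protocol Table 5.

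**Coverage.** Two million simulated trials per drift, on the normal scale; interval = estimate ± 1.96 SE at the stopping look.

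| Drift | All trials, lower bound obeyed | All trials, lower bound ignored | Final look only, obeyed | Final look only, ignored |
|---|---|---|---|---|
| 0 | 93.0% | 94.7% | 96.9% | about 95.7% |
| 1 | 91.4% | 93.2% | 99.6% | 97.0% |
| 2 | 91.7% | 92.9% | 98.4% | 96.5% |
| 2.845 | about 94% | about 94% | 94.7% | 94.0% |

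For larger effects the overall shortfall fades; coverage is 95.0% at drift 4.

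**Disagreement at the final look.** The confidence level matching 2.03 is 2Φ(2.03) - 1 = 95.76%. The probability of reaching the final look with 1.96 < Z ≤ 2.03 is 0.3% at drift 0, about 2.5% at drift 2 (near 50% power) and 1.7% at 2.845. Examples:
- 18/98 vs 30/98: difference 0.1224, pooled SE 0.0614, Z = 1.993 (fails). Wald: 0.1224 ± 1.96 × 0.0608 = 0.3 to 24.2 points.
- 17/105 vs 29/105: Z = 2.002 (fails). Wald 95% interval: 0.35 to 22.5 points.

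With multiplier 2.03 both intervals include zero.

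**Residual mismatch.** The Pearson Z uses the pooled variance and a Wald interval the unpooled one. For 17/98 vs 29/98, Z = 2.022 (fails), yet the unpooled lower limit at 2.03 is 0.12245 - 2.03 × 0.05991 = +0.08 points. With the pooled SE it is 0.12245 - 2.03 × 0.06054 = -0.05 points, which agrees with the test.

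**Estimate after early stopping.** At drift 2.845, 58% of trials stop early for efficacy, with a mean estimate about 1.43 times the truth (1.43 × 17.56 ≈ 25 points, where the truth is 17.56). Stops at the lower bound err the other way. Under the null with that bound obeyed, 42.7% of trials stop low, with a mean estimate of -1.48 final-look SEs.

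**The case against.** The strongest reply is that little is at stake. The Z bounds alone decide the primary result, type I error is preserved, and the interval is supplementary. The disagreement zone is narrow. The lowest coverage figures require the trial always to stop at the lower bound, whereas protocol 15.5 says only what crossing it would denote, and protocol Section 14 says the DSMB may recommend discontinuation. All of this stands, and it limits the size of the point. It does not remove it, because coverage is below 95% from the null to the design alternative even with the lower bound ignored.

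A reader might infer more than the documents support:
- *That the primary test is compromised.* It is not; only the reported interval and estimate are affected.
- *That the final-look interval under-covers in general.* Among trials reaching that look it covers above 95% for null to moderate effects and only slightly below 95% at the design alternative. Moving to 2.03 there gains agreement with the test, not coverage.
- *That every early stop inflates the estimate.* Only efficacy stops do.
- *That the exact interval falls short by a similar amount.* That branch was not computed, and exact intervals tend to be conservative. It is also unlikely to be used at the design rates: expected successes are 0.2478 × 0.286 × 97.86 ≈ 6.9 per arm at the first look and 0.2478 × 97.86 ≈ 24 at the final one, above the SAP's threshold of 5.

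**Conclusion.** The point holds, at moderate size. SAP 1.1.1 and protocol 15.1 attach a fixed-sample 95% interval to a five-look sequential test. Averaged over the design, and from the null to the design alternative, the shortfall is about 1 to 4 percentage points if the lower bound is obeyed and between a fraction of a point and about 2 if it is ignored. At the final look the issue is mainly a possible contradiction with the test, at most about a 1-in-40 event. The estimate after an efficacy stop is materially inflated, and the plan makes no provision for it. These figures rest on the normal approximation, the planned information fractions, a Wald interval, and, for the design alternative, the rates in protocol 15.6.1. The plan should be amended, but nothing here calls the primary decision rule into question.

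**What to change.** Amend SAP 1.1.1, its summary of changes and protocol 15.1 to name one of two intervals:

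1. a 95% interval from stagewise ordering, with a median-unbiased estimate; or
2. a repeated confidence interval whose multiplier is the upper (efficacy) bound of the look at which the trial stops, 2.03 at the final look. The lower bound must never serve as the multiplier: its magnitudes of 0.21 to 1.76 would give intervals narrower than the current one.

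Simply replacing 1.96 by 2.03 at every look is not enough; coverage would still be as low as 92.4% if the lower bound is obeyed.

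Also use the same variance form for test and interval, or state that the Z bound decides if they differ. If the exact branch is used, set its level to match the bound of that look.

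The cost is a sentence or two of text, with no extra participants. A repeated interval is 2.03/1.96 = 1.036, or about 3.6%, wider at the final look. After an early stop it is 21% (2.37/1.96) to 58% (3.09/1.96) wider. It is conservative, with simulated coverage of about 95% to 99%. The stagewise interval avoids most of that extra width.

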1.1.2 Secondary Analyses of Primary Outcome

In a secondary analysis, an alternative outcome variable will be created to represent the participant's community ambulation status at 16-week follow-up. This secondary variable will take the value of 'yes' if the participant was tested with the SMWT and walked 300 m or more in six minutes. The secondary variable will take the value of 'no' if 1) the participant was tested with the SMWT and walked less than 300 m in six minutes, 2) the participant was not tested with the SMWT and adjudication resulted in the participant's being classified as a treatment failure because of death, sickness, or gait speed < 0.6 m/s, or 3) the participant was tested with the SMWT but not according to protocol and adjudication resulted in the participant's being classified as a treatment failure, whatever the reason. The secondary variable will take the value of 'missing' if 1) the participant was not tested with the SMWT and adjudication resulted in the participant's being classified as a treatment failure based only on self- or proxy-reported walking limitation or 2) the participant was not tested with the SMWT (or the participant was tested but not according to protocol) and adjudication resulted in the participant's being classified as 'indeterminate'. All participants, including those with a missing value for the alternative outcome variable, will be included in the secondary analysis. Weights will be used to adjust for covariate imbalances between the groups due to chance or differential rates of indeterminate outcomes. For the PUSH group, the weight for each observation will be defined as the inverse probability that an observation would be assigned to the PUSH group given the covariates for that observation. This will effectively up-weight observations from groups with lower probability of being in PUSH. Similarly, for the PULSE group, the weight for each observation will be defined as the inverse probability that an observation would be assigned to the PULSE group given the covariates for that observation. The probability of being assigned to PUSH (or PULSE) will be estimated as a function of covariates based on a logistic regression model. Candidate variables for creating the weights will include age, sex, and type of hip fracture; baseline BMI, MNA[®]-SF score, CES-D score, 3MS score, distance walked in six minutes on SMWT, SPPB score, mPPT score, NHATS balance score, gait speed on 50-ft fast walk, and gait speed on 4-m usual walk; and the presence of cardiac disease, pulmonary disease, diabetes, and history of stroke or TIA at baseline. Variables will be ranked for inclusion based on the Beach-Meier approach (Beach 1989). A common rule of thumb for logistic regression models is that there should be at least 10 events and 10 non-events for every covariate in the model. We will follow that rule of thumb (based on the number of community ambulators observed in our sample) in deciding how many covariates to include in the model used to estimate weights.

Finally, we will perform a sensitivity analysis to assess the degree to which the conclusions of the analysis could be affected by biases due to data missing not at random. To do so we will use the methods described in Magder, 2003.

1.1.3 Assessment of effect modification by site, period, and patient characteristics

Study site will be investigated as a modifier of the effect of the intervention by testing a site-by-intervention interaction term on the risk difference scale based on a binary regression model

with an identity link. If there is evidence that study site is an effect modifier (i.e., $p < 0.1$ for the interaction term), we will report site-specific treatment effects.

In the fall of 2014, a decision was made to modify the frequency of intervention visits during the first 8 weeks from 3 per week to 2 per week. We will assess the impact of this protocol change on the intervention outcomes in a secondary analysis. To do so, assuming no significant interaction between site and intervention group, we will assess the statistical significance of the interaction between the period during which the participant was randomized (before vs after the protocol change) and treatment group. If there is a significant interaction, then we will make separate treatment group comparisons in the two periods (one comparison for participants randomized during the period when there were three sessions per week and another for participants randomized during the period when there were two sessions per week).

In addition, a series of analyses will be performed to examine the differential impact of the PUSH intervention relative to the PULSE intervention in subgroups defined by participant characteristics. To do this, a variable-by-intervention interaction term will be tested for each of the following variables:

1. Gender
2. Age at baseline (≥ 85 years versus 60-84 years)
3. Baseline depression (CES-D score ≥ 16 versus CES-D score < 16)
4. Baseline balance confidence (with median Activities-Specific Balance Confidence scale score as the cutpoint to define the subgroups)
5. Baseline nutritional status (MNA®-SF score < 8 versus MNA®-SF score ≥ 8)
6. Baseline cognitive status (3MS score < 91 versus 3MS score ≥ 91)
7. Baseline physical performance (SPPB score < 7 versus SPPB score ≥ 7)

If the interaction term for any of these subgroup variables is significant, results will be presented separately in strata of the subgroup variable.

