Using a group sequential design with four interim analyses (see Section 15.5), and assuming an overall loss to follow-up of 6.8% and treatment non-compliance of 12.2%, a total sample of 210 enrolled patients (105 patients per group) is sufficient to achieve over 80% power for the detection of a 20 percentage point difference between the groups, with 16% achieving the 300 m threshold of the SMWT in the PULSE group vs 36% in the PUSH group, using a one-sided 0.025 significance level. The power specified is for the detection of a time-specific difference at the 16-week follow-up. This calculation accounts for the sample size inflation of 2.4% needed to account for the group sequential design^{211,212} and for the impact of noncompliance on the variance of treatment differences under the assumption that non-compliers assigned to the PUSH group have an equal 16-week proportion achieving community ambulation as participants assigned to the PULSE group.^{214,215}

Table 5 shows the power to detect various between-group differences in proportions of community ambulators using a one-tailed test of the difference in proportions at the 2.5% significance level. The table indicates that the study has adequate power for detecting differences down to 20 percentage points.

Table 5. Power to Detect Difference in Proportions

True Difference in Proportion Achieving Community Ambulation at 16 Weeks	Power (%)
23 percentage points	89
22 percentage points	87
21 percentage points	84
20 percentage points	80
19 percentage points	76
18 percentage points	72
17 percentage points	68

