Assessment of Effect Modification of site, period (pre and post decreased visit frequency) and patient characteristics. (Section 1.1.3)	No details provided	Additional Details: Effect modification will be tested on the risk-difference scale based on a binary regression model with an identity link. Also, baseline physical performance as measured by the SPPB will be tested as a potential effect modifier.
Model-based estimates of Delayed and Sustained Effects on Primary Outcome (Section 1.2.1)	Longitudinal logistic regression for two time points (baseline, 16-week, 40-week) model fit with GEE to account for repeated measures from same individual	Changed to a longitudinal binary regression model with identity link and random effect for subject to account for repeated measures. Rationale: Estimates interpretable as rate differences.
Subject-based estimates of delayed and sustained effects on Primary Outcome (Section 1.2.1)	Not in original plan	3x3 table in each treatment group with rows indicating community ambulation at 16 weeks (yes, no, indeterminate) and columns indicating community ambulation at 40 weeks (yes, no, indeterminate).
Secondary and Tertiary Outcomes		
Longitudinal Data Analysis of quantitative secondary and tertiary outcomes. (Section 1.2.2)	Longitudinal Analysis based on three time points (baseline, 16-weeks, and 40-weeks) fit by GEE.	Changed from GEE to maximum likelihood with an unstructured variance. Rationale: A little more flexible than GEE and may adjust for baseline values better.
Sensitivity analysis to account for missing outcome data (Section 1.4)	Weighted Estimating Equations	Adjustment for covariates in the longitudinal regression model. Covariates chosen by a published method
Sensitivity analysis for non-adherence to protocol (removed)	Weighted analysis with weights based on inverse probability of treatment received as a function of covariates and treatment	Not included in new plan due in part to difficulty defining adherence.
Sensitivity analyses to variation between physical therapists or sites (Section 1.5)	Not in original plan	Rerun the analyses including a random effect for physical therapist or site.

Section 1. Detailed Statistical Analysis Plan

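### Subgroup effects are planned for presentation when the interaction test is significant, and no estimates are provided for when it is not

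*SAP*

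**What the plan says.** SAP 1.1.3 lists seven baseline characteristics (the six in Protocol 15.1 plus SPPB) and plans that "a variable-by-intervention interaction term will be tested for each of the following variables". The rule for reporting is: "If the interaction term for any of these subgroup variables is significant, results will be presented separately in strata of the subgroup variable". Protocol 15.1 has the same rule.

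Site is treated alike, with a stated threshold: "If there is evidence that study site is an effect modifier (i.e., $p < 0.1$ for the interaction term), we will report site-specific treatment effects". For the 2014 change in visit frequency, SAP 1.1.3 makes separate period comparisons if that interaction is significant. For period and for the seven characteristics, no significance level is given.

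The scale is fixed in the SAP's table of changes: "Effect modification will be tested on the risk-difference scale based on a binary regression model with an identity link". SAP Section 1 says that, apart from the primary test, "all statistical tests will be two-sided and will not be adjusted for multiple comparisons".

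Neither document says what is reported when an interaction is not significant. The commitments to give all treatment effects with 95% confidence intervals are in SAP 1.2.1 and 1.2.2. They cover the 40-week analysis and the secondary and tertiary outcomes, not the subgroup analyses.

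**The concern.** When an estimate appears only if its own test is significant, the estimates that appear are a biased sample. If no interaction exists, whatever appears is chance. If a moderate interaction exists, it appears only when chance has enlarged it. A trial sized for a main effect has little power for interactions, so both problems apply here.

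The purpose of these analyses is to see whether the effect of PUSH relative to PULSE differs between kinds of participant. A reader needs all the stratum estimates with their uncertainty to judge that. A non-significant interaction with an interval 48 points wide is not evidence of consistency, but without the interval the reader cannot see this.

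**Working it through.** **Inputs.** From Protocol 15.6.1: "a total sample of 210 enrolled patients (105 patients per group) is sufficient to achieve over 80% power" for 16% versus 36%, at one-sided 0.025, with 6.8% loss, 12.2% non-compliance and 2.4% group sequential inflation. PUSH non-compliers are assumed to have the PULSE rate.

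**Reproducing the plan's figure.** The effective difference is 0.20 × 0.878 = 0.1756, so the rates are 16% and 33.56%. The effective number per arm is 105 × 0.932 / 1.024 = 95.6. The two-proportion formula gives 80.8% power, against 80% in Protocol Table 5. For true differences of 23 down to 17 points it gives 89.5, 87.0, 84.1, 80.8, 77.1, 73.0 and 68.5%, against 89, 87, 84, 80, 76, 72 and 68%. The inputs are therefore read correctly. The documents give no power or error rate for the interaction tests.

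**Assumptions not in the documents.** A two-sided 0.05 threshold for the seven variables (0.10 as the alternative), independent tests, and the stratum splits and true interactions shown below.

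**False positives.**
- Seven tests at 0.05: 1 − 0.95^7 = 30%.
- Seven tests at 0.10: 1 − 0.90^7 = 52%.
- Seven plus period at 0.05 and site at 0.10: 1 − 0.95^8 × 0.90 = 40%.

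**Smallest estimate that reaches significance.** Evaluable participants per arm: 105 × 0.932 = 97.9. For a stratum holding a fraction f of each arm,

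SE² = [0.16 × 0.84 + 0.3356 × 0.6644] × [1/(97.9f) + 1/(97.9(1 − f))].

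The first bracket is 0.1344 + 0.2230 = 0.3574.

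| Split | SE (points) | Threshold at 0.05 (1.96 SE) | Threshold at 0.10 (1.645 SE) |
|---|---|---|---|
| 50:50 | 12.1 | about 24 | about 20 |
| 25:75 | 14.0 | about 27 | about 23 |
| 10:90 | 20.1 | about 39 | about 33 |

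At 0.05, all three exceed the 20-point main effect for which the trial is sized.

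**What is shown when an interaction is real** (50:50, 0.05, SE 12.1). With true interaction d, the upper-tail power is 1 − Φ(1.96 − d/SE), plus a small lower tail. The mean absolute estimate given significance follows from the truncated normal distribution.

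| True interaction (points) | Shown | Mean size when shown (points) | Inflation |
|---|---|---|---|
| 10 | 13% | about 30 | 3.0-fold |
| 20 | 38% | about 32 | 1.6-fold |
| 30 | 70% | about 36 | 1.2-fold |

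If the variance follows the stratum-specific rates, the chances of being shown become 13, 39 and 73%, and the inflation is almost the same. On that basis, a 25:75 split gives 11, 29 and 56%, with 3.5-, 1.8- and 1.3-fold inflation. A 0.10 threshold at 50:50 gives 21, 51 and 82%, with 2.7-, 1.5- and 1.1-fold inflation.

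**Balance confidence.** Protocol 10.4.3 and 11.1 drop this measure under version 11.0, and Protocol 15.6.2 expects about 160 participants for the dropped measures. After 6.8% loss that is 149, or 74.6 per arm. At the median split the SE is √(0.3574 × 2/37.3) = 13.8 points, and the 0.05 threshold is about 27 points.

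**The case against.** Much can be said for the plan. The variables and cutpoints are prespecified. The condition is a formal interaction test, not a search through within-stratum p-values, and that restrains subgroup claims. The analyses are secondary and cannot change the primary test. These points stand. They limit the selection but do not remove it.

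Three stronger readings are tempting, and the documents do not support them.

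- **That non-significant results will be concealed.** The text says if, not only if. It does not say that interaction p-values or the list of tests will be withheld. The documents support only that nothing is promised for these results.
- **That the report will consist mainly of spurious subgroups.** With no true interactions and seven independent tests at 0.05, there is about a 70% chance that none of the seven is shown. For a very large interaction the inflation is modest. Correlation among variables such as age, SPPB and balance confidence would also change the 30%.
- **That the test is invalid in small strata and needs the primary analysis's sparse-data rule.** SAP 1.1.1 has such a rule ("If the exploratory analyses reveal data sparseness") and 1.1.3 has none. But 1.1.3 names no test statistic; Wald tests are named only in 1.2.1 and 1.2.2. If a Wald test were used, simulation gives a true type I error of about 20, 15, 10 and 8% for strata of 8, 10, 14 and 20 of 196 participants, falling to 6.6% at 30 and 5.9% at 40. The documents give no stratum sizes, so the problem is not shown to arise. An expected-count-below-5 trigger would also be too broad. At a 16% PULSE rate it applies until a stratum holds 5/0.16 = 31 PULSE participants, about 32% of the arm, where the test is already close to its nominal level.

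**Conclusion.** The concern holds as a reporting defect. Followed as written, the plan commits to stratum effects after a significant interaction and to nothing otherwise, for the seven characteristics and likewise for site and period. For interactions up to about the size of the planned main effect, an estimate that passes a 0.05 threshold is either chance or inflated on average by about 1.6-fold or more.

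The sizes rest on an assumed threshold, independent tests, assumed splits and the planned response rates. The direction of the bias does not depend on them. The primary test and its conclusion are unaffected. This is a worthwhile, low-cost improvement, not a threat to the trial's main result.

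**What to change.** Change SAP 1.1.3 as follows.

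- For all seven variables, site and period, present within-stratum risk differences with 95% confidence intervals, cell counts, and the interaction estimate with its interval and p-value, whatever that p-value is.
- State how many interactions are tested and the threshold used for each, and label the analyses exploratory.
- Note that balance confidence is available only for participants consented before version 11.0 (about 160 before loss).
- Where a stratum proves very small, show the counts and do not rely on a Wald test. Do not adopt a blanket expected-count rule.

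With everything shown, nothing is selected on significance. The 95% interval for an interaction would have a half-width of about 24 points at 50:50, 27 at 25:75 and 39 to 41 at 10:90, and about 27 for balance confidence at the median split. That shows readers how little these data can say about effect modification.

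The cost is one table or forest plot and a few sentences. No new data or participants are needed.
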